**Post-Study adverse events and serious adverse events**

A post-study AE/SAE is defined as any event that occurs outside of the AE/SAE reporting period. Investigators are not obligated to actively seek AEs or SAEs in former study participants. However, if the investigator learns of any SAE at any time after a participant has been discharged from the study, and he/she considers the event reasonably related to the investigational product, the investigator will promptly notify the Study Contact for Reporting SAEs.

**Evaluation of adverse events and serious adverse events****Active questioning to detect adverse events and serious adverse events**

As a consistent method of collecting AEs, the participants should be asked a non-leading question such as:

*'Have you acted differently or felt different in any way since receiving the product or since the last visit?'*

When an AE/SAE occurs, it is the responsibility of the investigator to review all documentation (e.g. hospital progress notes, laboratory and diagnostics reports) relative to the event. The investigator will then record all relevant information regarding an AE/SAE in the eCRF. The investigator will attempt to establish a diagnosis pertaining to the event based on signs, symptoms, and/or other clinical information. In such cases, the diagnosis should be documented as the AE/SAE and not the individual signs/symptoms.

**Assessment of adverse events****Assessment of intensity**

The intensity of the following solicited AEs will be assessed as described:

The maximum intensity of local injection site redness/swelling will be scored as follows:

0: ≤ 20 mm

1: > 20 - ≤ 50 mm

2: > 50 - ≤ 100 mm

3: > 100 mm

The grade of fever will be scored as follows (oral temperatures\*):

1: ≥ 38.0°C (100.4°F) - ≤ 38.5°C (101.3°F)

2: > 38.5°C (101.3°F) - ≤ 39.0°C (102.2°F)

3: > 39.0°C (102.2°F) - ≤ 40.0°C (104°F)

4: > 40.0°C (104°F)

\*oral temperature=axillary temperature+0.2°C

The investigator will assess the maximum intensity that occurred over the duration of the event for all unsolicited AEs (including SAEs) recorded during the study. The assessment will be based on the investigator's clinical judgment.

The intensity should be assigned to one of the following categories:

- Grade 1 (mild) = An AE which is easily tolerated by the participant, causing minimal discomfort and not interfering with everyday activities.
- Grade 2 (moderate) = An AE which is sufficiently discomforting to interfere with normal everyday activities.
- Grade 3 (severe) = An AE which prevents normal, everyday activities
- Grade 4= An adverse event that is potentially life threatening.
- Grade 5=An AE which results in death.

An AE that is assessed as Grade 3 (severe) should not be confused with a SAE. Grade 3 is a category used for rating the intensity of an event; and both AEs and SAEs can be assessed as Grade 3. An event is defined as 'serious' when it meets one of the predefined outcomes.

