#### Time period for detecting and recording adverse events and serious adverse events

All AEs starting within 28 days following administration of the dose of the study product must be recorded into the appropriate section of the eCRF, irrespective of intensity or whether or not they are considered injection related.

The time period for collecting and recording SAEs and MAEs in all participants will begin at the first receipt of study product/comparator and will end on Day 364.

All AEs/SAEs leading to withdrawal from the study will be collected and recorded from the time of the first receipt of study product. SAEs that are related to the investigational product will be collected and recorded from the time of the first receipt of study product/comparator until the participant is discharged from the study.

In addition to the above-mentioned reporting requirements and in order to fulfill international reporting obligations, SAEs that are related to study participation (i.e. protocol-mandated procedures, invasive tests, a change from existing therapy) will be collected and recorded from the time the participant consents to participate in the study until she/he is discharged from the study.

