### **7.3 Participant contact of adverse events and serious adverse events**

#### **Participant contacts during the study**

After the initial AE/SAE report, the investigator is required to proactively follow each participant and provide additional relevant information on the participant's condition to the IRB.

All SAEs documented at a previous visit/contact and designated as not recovered/not resolved or recovering/resolving will be reviewed at subsequent visits/contacts until the end of the study.

With the exception of MAEs, all AEs documented at a previous visit/contact and designated as not recovered/not resolved or recovering/resolving will be reviewed at subsequent visits/contacts until 28 days after vaccination.

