#### **Participant contact after the participant is discharged from the study**

The investigator will follow participants:

- With SAEs, or participants withdrawn from the study as a result of an AE, until the event has resolved, subsided, stabilized, disappeared, or until the event is otherwise explained, or the participant is lost to participant contact, defined as four attempts to contact by phone/email at different times of the day have been unsuccessful and a letter has been sent to the address with no reply.
- With MAE until the end of the study or the participants are lost to participant contact.
- With other non-serious AEs, until Day 28 after injection or they are lost to participant contact.

If the investigator receives additional relevant information on a previously reported SAE, he/she will provide this information to the IRB using a paper SAE and/or pregnancy report as applicable.

The manufacturer of the investigational product may request that the investigator performs or arranges the conduct of additional clinical examinations/tests and/or evaluations to elucidate as fully as possible the nature and/or causality of the AE or SAE. The investigator is obliged to assist. If a participant dies during participation in the study or during a recognized participant contact period, the IRB will be provided with any available post-mortem findings, including histopathology.

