#### **8.2 Participant withdrawal**

Participants who are withdrawn because of SAEs/AEs must be clearly distinguished from participants who are withdrawn for other reasons. Investigators will follow participants who are withdrawn as result of a SAE/AE until resolution of the event. Withdrawals will not be replaced, unless the withdrawal is prior to the first dose of study vaccine.

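### Whole-event grading of unsolicited AEs cannot be met for non-serious, non-medically-attended events still open 28 days after a dose, because their review ends that day

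*Protocol*

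**What the plan says.** Four sets of rules in the protocol bear on this point.

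- **Grading.** Section 7.2, Assessment of intensity: "The investigator will assess the maximum intensity that occurred over the duration of the event for all unsolicited AEs". SAEs are included, and no exception is made for events still open at a cut-off. Assessment of outcomes, in the same section, asks for an outcome for each of these events and has codes for events that are unresolved or still resolving.
- **Onset window.** Section 7.2, time period for detecting and recording: "All AEs starting within 28 days following administration of the dose of the study product must be recorded".
- **End of review.** Section 7.3, contacts during the study: "With the exception of MAEs, all AEs documented at a previous visit/contact" and still unresolved "will be reviewed at subsequent visits/contacts until 28 days after vaccination". Section 7.3, contact after discharge, says the same: "With other non-serious AEs, until Day 28 after injection or they are lost to participant contact".
- **Exceptions.** SAEs "will be reviewed at subsequent visits/contacts until the end of the study", and beyond discharge until resolved or stabilised. MAEs are followed as well: "With MAE until the end of the study or the participants are lost to participant contact". Section 8.2 adds: "Investigators will follow participants who are withdrawn as result of a SAE/AE until resolution of the event".

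Two further places limit what can be captured later. Section 5.1 (Safety participant contacts) enters only SAEs and MAEs in the eCRF from the telephone follow-up. Table 3 in Section 7 likewise lists only SAEs and MAEs after the 28-day period.

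**The concern.** The onset window and the review window close on the same day. An AE that starts on Day 25 is admitted to the data set but has three days of planned observation. If it worsens afterwards without becoming serious, prompting a medical visit or causing withdrawal, no rule brings the higher grade into the AE record.

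The diary schedule sharpens this. Unsolicited AEs are collected by diary, and the diary is reviewed at the Day 28 visit (dose 1) or the Day 84 visit (dose 2). An event first documented at a visit on that day has no later AE review before the cut-off. The weekly contacts described in Section 3.3 ask about SAEs, MAEs and COVID-19 symptoms.

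At stake is the severity breakdown in Section 9.3.3 (mild, moderate, severe, and the combined moderate-or-severe class 'Significant') and the completeness of the outcome field. A maximum taken over part of an event can equal the true maximum or fall below it, but cannot exceed it, so any error runs one way. An analysis plan cannot repair this afterwards, because the follow-up will not have been collected.

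**Working it through.** The protocol gives no figure on this point, so there is nothing to reproduce. The check is first of the text and then of the possible scale.

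**Text.** Follow-up under the protocol for an unsolicited AE with onset inside 28 days of a dose and still open on day 28:

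| Type of event | Review continues? | Whole-event maximum observable? |
|---|---|---|
| Serious | Yes, to resolution or stabilisation (7.3) | Yes |
| Medically attended | Yes, to end of study (7.3) | Yes, unless open at study end |
| Leads to withdrawal | Yes, to resolution (8.2) | Yes |
| None of these | No, stops at day 28 (7.3) | No |

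Only the last row conflicts with the grading rule.

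**Scale, by illustration.** These inputs are assumptions, not taken from the documents: onset uniform over days 0 to 28, and exponential duration with mean m of 3, 7 or 14 days. The share of events still open at day 28 is

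P(open) = (m/28) × (1 − exp(−28/m)).

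- m = 3: 0.1071 × 0.9999 = 0.107
- m = 7: 0.25 × 0.9817 = 0.245
- m = 14: 0.5 × 0.8647 = 0.432

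If onset is concentrated early (exponential with mean 7 days, truncated at 28), the share is

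P(open) = [m/(7 − m)] × (e⁻⁴ − exp(−28/m)) / (1 − e⁻⁴), with limit 4e⁻⁴/(1 − e⁻⁴) at m = 7.

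- m = 3: 0.75 × 0.01823/0.98168 = 0.014
- m = 7: 4 × 0.01832/0.98168 = 0.075
- m = 14: 2 × 0.11702/0.98168 = 0.238

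These are open events, not misgraded ones. Misgrading also needs the peak to fall after day 28. With uniform onset:

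- Peak a quarter of the way through the event (replace m by m/4 in the first formula): 2.7%, 6.2% and 12.5% for m = 3, 7 and 14.
- Peak equally likely at any point of the event (simulation of 2,000,000 events): 5.3%, 12.4% and 23.5%.

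Under these assumptions, even the late-peak shares are upper limits on misgrading. They still include serious, medically attended and withdrawal-related events, which remain under review, and a late peak changes the record only if it crosses a grade boundary.

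**The case against.** The strongest reply is that this is a small wording gap, and much of that reply stands. A reader might infer five stronger things that the protocol does not support.

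- **That review of all non-serious AEs stops at day 28.** It does not. The sentence that sets the stop exempts MAEs, and under Section 7.2 (Medically attended AEs) any unscheduled medical contact counts. AEs leading to withdrawal are also followed to resolution.
- **That open events are closed as resolved.** The outcome list has codes for unresolved and resolving events. Such a code is an accurate status at last review; what is missing is the final status.
- **That the primary safety result is biased.** Section 9.3.3 defines that endpoint as the incidence of unsolicited AEs within 28 days. Incidence depends on onset, and all onsets in the window are recorded.
- **That the severity summary is known to be biased low.** The documents give no durations or peak times, so only the direction of a possible error is established. The 'Local' and 'General' aggregates are also built on the event classes that Section 7.1 solicits over seven days. Unsolicited events enter only through the wider statement that all events are graded for severity.
- **That the second-injection check relies on information four weeks old.** Table 1 schedules medical history, intercurrent conditions and contraindications at the Day 56 visit, and Section 6.2 has intercurrent conditions verified at every contact after the first injection.

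It can also be said that the grading rule may simply mean the peak seen while the event was under review. That reading would remove the conflict, but the text refers to the duration of the event, so it needs to be written down.

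**Conclusion.** The conflict is real but narrow. For unsolicited AEs that are neither serious nor medically attended and do not lead to withdrawal, the whole-event grading rule in Section 7.2 cannot be met once the event is open 28 days after a dose, because Section 7.3 ends its review that day. The primary incidence endpoint is untouched. The descriptive severity breakdown can err only downward, and some outcomes will lack a final status.

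The size cannot be derived from the documents. The illustrative shares of open events, from about 1% to 43%, depend on assumed onset and duration and overstate misgrading. The real exposure is mainly a mild event that becomes moderate or severe after day 28 without medical attention, which is probably uncommon. The point is worth correcting because the trial is centred on safety and the correction is cheap, not because a conclusion is likely to change.

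**What to change.** Reconcile the recording, intensity and outcome rules in Section 7.2 with the two follow-up rules in Section 7.3.

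- **Preferred.** Re-check any AE with onset within 28 days of a dose that is still open at the Day 28 or Day 84 visit at contacts already scheduled: the Day 56 visit, the 4-weekly calls and the Week 24 visit. Enter the final maximum grade and outcome in the eCRF, and amend Section 5.1 and Table 3 to allow that entry. Keep the 28-day onset window for counting incidence.
- **If the sponsor keeps the 28-day stop.** Define intensity in Section 7.2 as the maximum observed up to that cut-off, and flag events ongoing at the cut-off in the severity tables.

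The preferred change costs protocol wording and a little data entry at existing contacts, and the severity figures may become slightly less favourable. The alternative costs wording and a table flag, but leaves the late course of these events unobserved.

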### **Assessment of causality**

The investigator is obligated to assess the relationship between investigational product and the occurrence of each AE/SAE. The investigator will use clinical judgment to determine the relationship. Alternative plausible causes, such as natural history of the underlying diseases, concomitant therapy, other risk factors, and the temporal relationship of the event to the investigational product will be considered and investigated. The investigator will also consult the IB and/or PI to determine his/her assessment.

There may be situations when a SAE has occurred, but the investigator has minimal information to include in the initial SAE report. However, it is very important that the investigator always assesses causality for every event prior to submission of the SAE report. The investigator may change his/her opinion of causality in light of participant contact information and update the SAE information accordingly. The causality assessment is one of the criteria used when determining regulatory reporting requirements.

In case of concomitant administration of multiple products, it may not be possible to determine the causal relationship of general AEs to the individual products administered. The investigator should, therefore, assess whether the AE could be causally related to injection rather than to the individual products.

All solicited local (injection site) reactions will be considered causally related to injection. Causality of all other AEs should be assessed by the investigator using the following question:

*Is there a reasonable possibility that the AE may have been caused by the investigational product?*

**YES:** There is a reasonable possibility that the product(s) contributed to the AE.

**NO:** There is no reasonable possibility that the AE is causally related to the administration of the study product(s). There are other, more likely causes and administration of the study product(s) is not suspected to have contributed to the AE.

If an event meets the criteria to be determined as 'serious', additional examinations/tests will be performed by the investigator in order to determine ALL possible contributing factors for each SAE.

Possible contributing factors include:

- Medical history.
- Other medication.
- Protocol-required procedure.
- Other procedure not required by the protocol.
- Lack of efficacy of the product, if applicable.
- Erroneous administration.
- Other cause (specify).

### **Assessment of outcomes**

The investigator will assess the outcome of all unsolicited AEs (including SAEs) recorded during the study as:

- Recovered/resolved.
- Recovering/resolving.
- Not recovered/not resolved.
- Recovered with sequelae/resolved with sequelae.
- Fatal (SAEs only).

### **Medically attended AEs (MAEs)**

For each solicited and unsolicited symptom the participant experiences, the participant will be asked if they received medical attention defined as hospitalisation, or an otherwise unscheduled visit to or from medical personnel for any reason, including emergency room visits. This information will be recorded in the in the eCRF.

### **Prompt reporting of SAE, SUSAR and other events to IDMC, Research Ethics Board (IRB)**

SAEs will be reported promptly to the Independent Data Monitoring Committee and IRB within the timeframes described in this protocol once the investigator determines that the event meets the protocol definition of a SAE. SAEs will be collected throughout the study. If an SAE is confirmed as a SUSAR, then the sponsor will report it to the IDMC.

TABLE 4. TIMEFRAMES FOR SUBMITTING SAEs TO RESEARCH ETHICS BOARD AND STUDY FARMACOVIGILANCE UNIT

Type of Event	Initial Reports		Participant contact of Relevant Information on a Previous Report	
	Timeframe	Documents	Timeframe	Documents
SAEs	24 hours*	SAE report	24 hours*	SAE report

\* Timeframe allowed after receipt or awareness of the information.

**Completion and transmission of SAE reports**

Once an investigator becomes aware that a SAE has occurred in a study participant, the investigator (or designate) must complete the information in the SAE report as thoroughly as possible with all available details of the event, **WITHIN 24 HOURS**. Even if the investigator does not have all information regarding a SAE, the report should still be completed within 24 hours. Once additional relevant information is received, the report should be updated **WITHIN 24 HOURS**. The investigator will always provide an assessment of causality at the time of the initial report.

**Updating of SAE information after freezing of the participant's eCRF**

When additional SAE information is received after freezing of the participant's eCRF, new or updated information should be recorded on a paper report, with all changes signed and dated by the investigator. The updated report is provided to the IRB.

**Regulatory reporting requirements for serious adverse events**

The investigator will promptly report all SAEs to the in accordance with the procedures detailed in this protocol. Fundación Huésped as the clinical trial sponsor, has a legal responsibility to promptly notify the appropriate health agency about the safety of a product under clinical investigation. Prompt notification of SAEs by the investigator to the Study Contact for Reporting SAEs is essential so that legal obligations and ethical responsibilities towards the safety of other

participants are met. The purpose of the report is to fulfill specific regulatory and GCP requirements, regarding the product under investigation. All of these notifications will occur within 24 hours of the Investigator becoming aware of the SAE.

### **7.3 Participant contact of adverse events and serious adverse events**

#### **Participant contacts during the study**

After the initial AE/SAE report, the investigator is required to proactively follow each participant and provide additional relevant information on the participant's condition to the IRB.

All SAEs documented at a previous visit/contact and designated as not recovered/not resolved or recovering/resolving will be reviewed at subsequent visits/contacts until the end of the study.

With the exception of MAEs, all AEs documented at a previous visit/contact and designated as not recovered/not resolved or recovering/resolving will be reviewed at subsequent visits/contacts until 28 days after vaccination.

#### **Participant contact after the participant is discharged from the study**

The investigator will follow participants:

- With SAEs, or participants withdrawn from the study as a result of an AE, until the event has resolved, subsided, stabilized, disappeared, or until the event is otherwise explained, or the participant is lost to participant contact, defined as four attempts to contact by phone/email at different times of the day have been unsuccessful and a letter has been sent to the address with no reply.
- With MAE until the end of the study or the participants are lost to participant contact.
- With other non-serious AEs, until Day 28 after injection or they are lost to participant contact.

If the investigator receives additional relevant information on a previously reported SAE, he/she will provide this information to the IRB using a paper SAE and/or pregnancy report as applicable.

The manufacturer of the investigational product may request that the investigator performs or arranges the conduct of additional clinical examinations/tests and/or evaluations to elucidate as fully as possible the nature and/or causality of the AE or SAE. The investigator is obliged to assist. If a participant dies during participation in the study or during a recognized participant contact period, the IRB will be provided with any available post-mortem findings, including histopathology.

#### **7.4 Treatment of adverse events**

Treatment of any AE is at the sole discretion of the investigator and according to current good medical practice. Any medications administered for the treatment of an AE should be recorded in the participant's eCRF.

#### **Participant card**

Study participants must be provided with the telephone number of the main contact for information about the clinical trial. Participants must be instructed to keep participant cards in their possession at all times.

The investigator (or designate) must therefore provide a “participant card” to each participant. In an emergency situation this card serves to inform the responsible attending physician that the participant is in a clinical study and that relevant information may be obtained by contacting the investigator.

